5.1 Conventions

The precision of original measurements will be maintained in summaries, when possible. Means, Q1, medians, Q3 and standard deviations will be presented with an increased level of precision; means and Q1, medians, Q3 will be presented to one more decimal place than the raw data, and the standard deviations will be presented to two more decimal places than the raw data.

Summaries of continuous variables that have some values recorded using approximate values (e.g., < or >) will use imputed values. The approximate values will be imputed using the closest exact value for that measurement. For tables where rounding is required, rounding will be done to the nearest round-off unit. For example, if the round-off unit is the ones place (i.e., integers), values $\geq XX.5$ will be rounded up to $XX+1$ while values $< XX.5$ will be rounded down to XX .

For percentages, unless they are calculated to be exactly 0% or 100%, values of very small or very large percentages will be reported as $<0.1\%$ and $>99.9\%$. For by-visit tables, percentages will be based on available data and denominators will generally exclude missing values. For frequency counts of categorical variables, categories whose counts are zero will be displayed for the sake of completeness. For example, if none of the subjects discontinue due to “lost to follow-up” this reason will be included in the table with a count of 0.

5.2 Standard Calculations

Variables requiring calculation will be derived using the following formulas:

- **Baseline** - A baseline value, unless specified otherwise, is the last non-missing value recorded prior to the first dose of study drug. If an assessment has both a

date and time that exactly match the date and time of first dose of study drug, the assessment will be counted as baseline.

- **Study day** For a given date (*date*), study day is calculated as days since the date of first dose of study drug (*firstdose*):

Study day = $date - firstdose + 1$, where $date \geq firstdose$

Study day = $date - firstdose$, where $date < firstdose$

Study day 1 is defined as the day of study drug administration.

- **Hours** Durations, expressed in hours, between one hour (*hour1*) and another later hour (*hour2*) are calculated using the following formula: duration in hours = $(hour2 - hour1 + 1)$.
- **Days** Durations, expressed in days, between one date (*date1*) and another later date (*date2*) are calculated using the following formula: duration in days = $(date2 - date1 + 1)$.
- **Weeks** Durations, expressed in weeks, between one date (*date1*) and another later date (*date2*) are calculated using the following formula: duration in weeks = $(date2 - date1 + 1) / 7$.
- **Months** Durations, expressed in months, between one date (*date1*) and another later date (*date2*) are calculated using the following formula: duration in months = $(date2 - date1 + 1) / 30.4375$.
- **Years** Durations, expressed in years, between one date (*date1*) and another later date (*date2*) are calculated using the following formula: duration in years = $(date2 - date1 + 1) / 365.25$.
- **Body Mass Index (BMI)** - $BMI (kg/m^2) = weight (kg) / [(height (cm) / 100]^2$

Note that age on consent date is collected on the CRF and will not be calculated.

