7.3 Demographic and Baseline Characteristics

Demographic variables to be summarized include the following: date of signing the informed consent, age at informed consent (in years), gender, ethnicity, race, smoking status, height (in cm), weight (in kg), and body mass index (BMI). The BMI will be calculated.

Baseline characteristics, which includes information from the dental surgical procedure, will be summarized for the following: number of molars extracted, impacted molars classification, impacted molar position, planned surgical procedure, duration of surgery (minutes), amount of Lidocaine used during of surgery (mg), time from end of surgery to first dose of study medications (hours), and baseline pain intensity (both on the numeric 11-point rating scale and as categorized as none/mild/moderate/severe).

Demographic and baseline characteristics will be summarized for all the analysis populations (FAS, PPS and Safety Set).

The frequencies and percentages of subjects in the following categories of smoking status will be summarized: current smokers (every day or on some days per week), recent former smokers (smoked within the last 12 months), long-term former smokers (smoked 1 to more than 15 years ago), and never smoked regularly. The number of cigarettes/cigars/pipes smoked per week will be displayed in the listing for current smokers.

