8. EFFICACY ANALYSES

8.1 Efficacy Variables

8.1.1 Primary Efficacy Variable

The primary endpoint of the trial is 4-hour Total Pain Relief (TOTPAR4). TOTPAR4 is a time-weighted measure of Area under the Longitudinal Pain Relief Curve (AUC) up to 4 hours and is a summary measure that integrates serial assessments of a subject's pain over the duration of 4 hours after first dose (in [Appendix A](#)).

In general, the Total Pain Relief (TOTPAR) from the first administration of IMP to a fixed time-point, j , will be defined as:

$$\text{TOTPAR}_j = \sum W_i * \text{PR}_i, \text{ with } i \leq j$$

where the \sum sums over all observations collected from 0.25 hours after first IMP administration to Hour j and W_i is the time elapsed from the previous observation of pain relief PR_{i-1} to the current observation PR_i . For example, The TOTPAR4 will be calculated as a weighted sum of the observed pain relief scores for the first 4 hours after first dose with weights proportional to the duration of time since the last pain relief assessment.

For the first pain relief assessment, time (hours) elapsed since previous observation is time since first dose of IMP. Pain relief assessments after start of rescue medication intake will be set to missing and will be imputed as described in Section 8.3.

Minimum and maximum potential value for TOTPAR4 are 0 and 16 points, corresponding to a value of 0 (none) or 4 (complete) at all pain relief assessments in the first 4 hours after first dose, respectively.

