8.1.3 Additional Efficacy Outcomes

The following parameters will also be summarized:

- Pain relief score after first dose over time (in [Appendix A](#))
- Pain intensity score after the first dose over time (based on NRS) (in [Appendix A](#))
- Pain Intensity Difference (PID, NRS) after first dose over time (in [Appendix A](#))
- Peak pain relief score
- Peak pain intensity difference score
- Time to request the first dose of rescue medication (in [Appendix A](#))
- Time to peak pain relief score
- Time to peak pain intensity difference score

Pain relief, pain intensity, and PIDs are defined as described above in Section 8.1.2.

The peak pain relief score is the maximum pain relief assessment for the subject during the 16 observation period (prior to the use of any rescue medication), while time to peak pain relief score is the time from first administration of IMP to the first occurrence of that peak relief score, in hours. The peak pain intensity difference is the maximum pain intensity difference for the subject during the 24 observation period (prior to the use of any rescue medication), while time to peak pain intensity difference is the time from first administration of IMP the first occurrence of that peak intensity difference, in hours.

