9.4 Exploratory Efficacy Analyses

The following exploratory analyses will be performed on these additional efficacy outcomes:

1. Pain Relief Score after first dose over time
2. Pain Intensity Score after the first dose over time (based on NRS)
3. Pain Intensity Difference (PID, NRS) after first dose over time
4. Peak pain relief score
5. Peak pain intensity difference
6. Time to request the first dose of rescue medication
7. Time to peak pain relief score
8. Time to peak pain intensity difference

Pain relief scores, pain intensity scores, and pain intensity difference scores over time will be analyzed at each time point using the same ANCOVA model described for the primary endpoint, TOTPAR4. Peak pain relief score and peak pain intensity difference will also be analyzed using the same ANCOVA model described for the primary endpoint.

Time to peak pain relief score and time to peak pain intensity difference be presented using Kaplan-Meier plots. Medians will be compared across the groups using Wilcoxon Log-rank test, and Hazard Ratios (HR) will be compared across the groups using Cox Hazard Ratio model. The summaries will include quartiles and HR and their corresponding 95% confidence intervals along with the p-values. Please see [Appendix B](#) for details on the determination of event and censoring time points. Note that alpha levels for exploratory analyses are not adjusted for multiple comparisons.

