Appendix A: Definitions for Efficacy Endpoints

1. Pain Intensity and Numerical Rating Scale (NRS)

11-point Numerical Rating Scale (NRS) is used to evaluate pain intensity.

Pain Intensity Rating Scale

Please rate your pain by selecting the one number that best describes how much pain you have right now:

Pain intensity: Subjects will be asked to assess their current pain by selecting a number corresponding to their pain, with anchors at 0 for “no pain” and 10 for “pain as bad as you can imagine”. The subjects will be asked to answer the following question:

“Please rate your pain by selecting the one number that best describes how much pain you have right now”.

Pain intensity will be categorized as:

- None NRS score of 0
- Mild NRS score of ≥ 1 and < 5
- Moderate NRS score of ≥ 5 and ≤ 6
- Severe NRS score of ≥ 7

NRS pain scores will be assessed before the first dose of IMPs, and 15, 30, 45, 60, and 90 minutes (± 2 minutes), and 2, 3, 4, 5, 6, 7, 8, 16, and 24 hours (± 6 minutes) after the first dose of IMPs.

2. Pain Relief and Verbal Rating Scale (VRS)

The subject's pain relief will be assessed using a 5-point Verbal Rating Scale (VRS) by completion of the following statement.

"My relief from starting pain is"

- None (0)
- A little (1)
- Some (2)
- A lot (3)
- Complete (4)

Pain relief will be assessed 15, 30, 45, 60, and 90 minutes (± 2 minutes), and 2, 3, 4, 5, 6, 7, 8, and 16 hours (± 6 minutes) after administration of the first dose of IMPs.

3. Total Pain Relief at 4, 6, and 8 hours (TOTPAR4, TOTPAR6, and TOTPAR8)

Total Pain Relief (TOTPAR) will be defined as $\sum PR_t \times$ [time (hours) elapsed since previous observation] where PR_t is the Pain Relief at time point t in comparison to the assessment before administration of IMPs. The TOTPAR will be calculated at 4, 6, and 8 hours.

4. Peak Pain Relief

Peak pain relief will be defined as the maximum pain relief score for the subject over the 16 hours after administration of the first dose of IMPs, but prior to the intake of any rescue medications.

5. Pain Intensity Difference (PID)

Pain Intensity Difference (PID_t) will be defined as the difference between baseline pain intensity and pain intensity at time point t (e.g., baseline score - time point t score). The PID (11-point NRS) compared to baseline at 15, 30, 45, 60, and 90 minutes, and at 2, 3, 4, 5, 6, 7, 8, and 24 hours will be calculated.

6. Summed Pain Intensity Difference (SPID)

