Summed Pain Intensity Difference (SPID) will be defined as $\sum PID_t \times$ [time (hours) elapsed since previous observation]. The SPID at 4, 6, 8, and 24 hours post-dose will be calculated.

7. Peak Pain Intensity Difference

Peak pain intensity difference will be defined as the maximum pain intensity difference for the subject over the 24 hours after administration of the first dose of IMPs, but prior to the intake of any rescue medications.

8. Subject's Global Evaluation of the Treatment (Likert Scale)

The subject's overall impression (overall assessment) of the analgesic efficacy of the IMPs will be obtained at 8 hours after the first dose of IMPs or before first intake of rescue medication (whichever happens first) and at 24 hours after the first dose of IMPs. Subjects will be asked the following question and will be requested to also record the time at which it was answered:

"How would you rate the study medication you received for pain?"

- Excellent (4)
- Very good (3)
- Good (2)
- Fair (1)
- Poor (0)

9. Time to Achieve a 50% Reduction of Baseline Pain

The subject's 50% reduction of starting pain will be assessed by answering the following statement with YES or NO:

"My starting pain is at least half gone"

The subject should be reminded that each assessment should be performed independently of previous assessments.

10. Time to Onset of First Perceptible and Meaningful Pain relief

At the time of dosing with the IMPs, the investigator will start 2 stopwatches for each subject. The subject will be instructed to stop the first stopwatch at the time of first perceptible pain relief and the second stopwatch at the time when they first experience meaningful pain relief. The definitions of the perceptible and meaningful pain relief are as follows:

Time to onset of first perceptible pain relief

When the subject begins to feel any pain-relieving effect from the IMPs.

Subject instruction:

"I would like you to stop the stopwatch when you first feel any pain relief whatsoever. This does not mean you feel completely better, although you might, but when you first feel any difference in the pain that you have had."

Time to onset of meaningful pain relief

When the subject feels their pain relief is meaningful to them.

Subject instruction:

“I would like you to stop the stopwatch when you have meaningful pain relief. That is, when the relief is meaningful to you.”

11. Time to Request and Intake of First Rescue Medication

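### SAP 5.2 adds one hour to durations in hours, and SAP 5.4 both removes assessments with a partial clock time and completes that time (minor)

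*SAP*

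**What the plan says.** **Durations.** SAP 5.2 opens with a general instruction: "Variables requiring calculation will be derived using the following formulas". Among the formulas, durations in hours "are calculated using the following formula: duration in hours" = hour2 - hour1 + 1. This has the same form as the line for days that follows it.

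Two places report derived durations in hours without giving arithmetic:

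- SAP 7.3 lists, among the baseline characteristics, "time from end of surgery to first dose of study medications (hours").
- SAP 8.1.3 defines time to peak pain relief as the "time from first administration of IMP to the first occurrence of that peak relief score, in hours", and time to peak pain intensity difference in the same way. Appendix A sets the peaks as the "maximum pain relief score for the subject over the 16 hours after administration of the first dose of IMPs" and the "maximum pain intensity difference for the subject over the 24 hours after administration of the first dose of IMPs".

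The TOTPAR weights (SAP 8.1.1) and SPID weights (SAP 8.1.2) have their own definition: time elapsed since the previous observation. SAP 8.1.1 adds: "Minimum and maximum potential value for TOTPAR4 are 0 and 16 points".

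**Partial times.** SAP 5.4 refers to SAP 8.3 for TOTPAR imputation. It then says that an assessment with a partial or missing time is unreliable and is removed. The next sentence sets out a process for assessments with partial times. Before 1 hour, if the hour is missing, the minutes are used. After 1 hour, missing minutes are taken from the prior sampling time, failing that from a later one, and failing that set to 0. SAP 8.3 removes assessments with a missing date or time and does not mention partial times.

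**The concern.** The +1 is right when the first and last day both count. Between two clock times it adds an hour that did not pass. SAP 7.3 gives no other rule for surgery-to-dose time, so a programmer who follows the plan prints a wrong value for every subject. The size is noticeable: the protocol (section 10.2) requires qualifying pain within 4 hours after surgery, with dosing as soon as it is confirmed. A dose at 4 h would print as 5 h and look like a deviation.

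In SAP 5.4 the same record is both dropped and kept. If it is dropped, its score becomes intermittent missing data and SAP 8.3.1 replaces it with the last observation. If its time is completed, the observed score stays. Two programmers can therefore obtain different TOTPAR values from one record, and TOTPAR4 is the primary endpoint.

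**Working it through.** **(a) The +1**

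Inputs: the SAP 5.2 formula; pain relief at 15, 30, 45, 60 and 90 minutes and 2, 3 and 4 hours (protocol 7.1, SAP Appendix A item 2); relief scored 0 to 4; stated TOTPAR4 maximum of 16 (SAP 8.1.1).

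1. Reproduce the plan's figure. With plain differences the weights sum to 4 × 0.25 + 2 × 0.5 + 2 × 1 = 4.0 h, and the maximum is 4 × 4.0 = 16, as stated.
2. With +1 on each of the 8 weights the sum is 4.0 + 8 = 12 h and the maximum is 4 × 12 = 48. So the plan's own figure uses plain elapsed time, and the SAP 5.2 formula is not what drives the primary endpoint.
3. Surgery-to-dose time under SAP 5.2: the excess is (hour2 - hour1 + 1) - (hour2 - hour1) = 1 h for every subject. Thus 0.5 h prints as 1.5 h, 3.5 h as 4.5 h, and 4 h as 5 h (1/4 = 25% too long).
4. Times to peak, only if a programmer applies the general formula: the earliest value prints as 0.25 + 1 = 1.25 h, and the latest as 16 + 1 = 17 h (relief) and 24 + 1 = 25 h (intensity difference). The last two fall outside the periods in Appendix A.
5. Effect on comparisons: (mean A + 1) - (mean B + 1) = mean A - mean B. Adding a constant leaves the order of event times unchanged, so log-rank and Cox results do not change. Means, medians, quartiles and Kaplan-Meier time axes move by 1 h.

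**(b) Partial times**

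SAP 5.4 set against the cases that it names (hour present with minutes missing, or the reverse):

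| Time point | Hour missing | Minutes missing |
|---|---|---|
| 15, 30, 45 min | use the minutes | no rule |
| 60 min | no rule | no rule |
| 90 min onward | time stays missing | copy minutes from another time point, or set to 0 |

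The removal sentence covers every cell of this table as well, so each completed time contradicts it.

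Illustrative record (assumed scores): 0, 0, 1, 1, 2, 3, 3, 2 at the eight times, with the 90-minute time lacking its minutes.

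1. Keep the score at nominal weights: 0.25 × (0 + 0 + 1 + 1) + 0.5 × 2 + 0.5 × 3 + 1 × 3 + 1 × 2 = 8.0.
2. Remove it, then LOCF: the 90-minute score becomes 1, so 0.5 × 2 becomes 0.5 × 1, and the total is 7.5.
3. Largest change from one such score: 4 points × 1 h = 4 points at 3 h or 4 h, which is 4/200 = 0.02 in the mean of a 200-subject arm. At 90 minutes or 2 h it is 4 × 0.5 = 2 points, or 2/200 = 0.01.
4. The documents do not say how many partial times to expect. For scale, a 0.5-point change in one subject moves a 200-subject mean by 0.5/200 = 0.0025. To move it by 0.15, one tenth of the 1.5-point margin, 0.15/0.0025 = 60 of 200 subjects would need such a change, all in the same direction.

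The copy-the-minutes step is also poor in itself. At 90 minutes and at 2 h the prior assessment is half an hour earlier, so its clock minutes are about 30 minutes off. The allowed windows make this 26 to 34 minutes at 90 minutes and 22 to 38 minutes at 2 h.

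**The case against.** **Times to peak.** They are worded as elapsed time from first dose, within 16 h and 24 h periods. By the logic that exempts TOTPAR and SPID, they should be exempt too. This largely stands: the shift there is only possible. SAP 9.4 also treats these endpoints as exploratory ("The following exploratory analyses will be performed on these additional efficacy outcomes"). Surgery-to-dose time remains directly exposed.

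**Validation.** Independent programming checks and senior review (SAP 5) may catch the +1. They may, but those checks include consistency with the plan, and a program with the +1 is consistent with it.

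**Partial times.** The pointer to SAP 8.3 favors removal for TOTPAR. Subjects are on site for the first 8 hours (protocol 10.2), the booklet is collected before they leave (protocol 11.1.2.1), and missing or inconsistent entries raise automatic queries (protocol 13.3). This stands as a reason to expect few such records. It does not settle the conflict, because SAP 8.3 names missing times and not partial ones.

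A reader might also infer stronger points that the documents do not support:

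- *The +1 inflates TOTPAR4 or SPID.* Their weights are defined separately, and the maximum of 16 excludes it for TOTPAR4.
- *Durations are coarsened to whole clock hours.* SAP 5.4 describes a 24-hour clock with hours and minutes, and nothing says that minutes are dropped.
- *SAP 5.4 imputes scores.* It completes the clock time only; the score is kept or removed.
- *Copied minutes move TOTPAR4.* With actual-time weights the example would give 8.5 (dose at 10:00) or 7.5 (dose at 10:40). But with the 6-minute window at 4 h, such weights could sum to 4.1 h and give a maximum of 4 × 4.1 = 16.4. The exact 16 speaks for nominal weights, under which copied minutes cannot change TOTPAR4.

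**Conclusion.** Both statements are wrong as written, and both are minor.

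(a) Followed literally, SAP 5.2 makes surgery-to-dose time exactly 1 h too long for every subject. Other durations in hours without their own arithmetic, such as the times to peak, are exposed only if a programmer falls back on the general formula. TOTPAR and SPID are not affected, and no test or arm difference changes.

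(b) SAP 5.4 contradicts itself on partial times and leaves gaps at 60 minutes and, for missing minutes, at 15, 30 and 45 minutes. The choice between keeping and removing changes an affected subject's TOTPAR4 by 0.5 point in the example and by at most 4 points for a single score. This rests on nominal weights and on illustrative scores. The number of affected records is not given; on-site assessment and data queries should keep it small. Treatment is blinded, so similar rates across arms would largely cancel in the difference. No primary conclusion is at risk.

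**What to change.** - SAP 5.2: define duration in hours as (datetime2 - datetime1) in minutes / 60, with no +1. Add that SAP 8.1.1, 8.1.2 and Appendix A govern the TOTPAR and SPID weights.
- SAP 5.4 and 8.3: state one rule for partial times at every time point, including 60 minutes and minutes missing before 1 hour. Either keep the score at its nominal time, or remove it and name partial times in SAP 8.3. Delete the copy-the-minutes step in both cases.

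The cost is a few SAP lines before database lock, with no change to data collection. Keeping the score at nominal time has a small downside: nominal and actual time can differ by the allowed window (2 minutes up to 90 minutes after dose, 6 minutes from 2 h on), or by more if the assessment was out of window. Removal instead replaces an observed score with the last earlier one.

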5.3 Handling Partial Dates for Adverse Events and Medications

If only a partial date is available and is required for a calculation, the following standards will be applied:

- Start dates
 - a. For missing start day only - Day will be imputed as the first day of the month (i.e., 1) with the following exception: if the partial date falls in the same month and year as the date being used in the calculation (e.g., first dose date, informed consent date), then the partial date will be imputed to equal the date being used for the calculation.
 - b. For missing start day and month - Day and month will be imputed as the first day of the year (i.e., 1 January) with the following exception: if the partial date falls in the same year as the date being used in the calculation (e.g., first dose date, informed consent date), then the partial date will be imputed to equal the date being used for the calculation.
- Stop dates
 - a. For missing stop day only - Day will be imputed as the last day of the month (i.e., 28, 29, 30, or 31)
 - b. For missing stop day and month - Day and month will be imputed as the last day of the year (i.e., 31 December)

A completely missing start date will be imputed as first dose date of study medication and a completely missing end date will be imputed as study completion date.

The date of last dose of study drug will be taken from the Study Exit Status CRF page whenever available. If this is missing, then the last visit date, excluding the follow-up visit, will be used, unless a blinded data review indicates it was earlier.

Any partial dates will be displayed in data listings without imputation of missing days and/or months (e.g., MAR2016 for missing day, and 2015 for day and month both missing).

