7.12 Prior and Concomitant Medications

Verbatim terms on case report forms will be mapped to Anatomical Therapeutic Chemical (ATC) class and Generic Drug Names using the World Health Organization (WHO) dictionary (version March 2016).

For the purposes of data reporting by the site, all medications used 14 days prior to enrollment and up to the time of surgery are considered prior medications. Concomitant medications are all medications not stopped before start of surgery or newly added thereafter. Prior medications and concomitant medications will be summarized separately for each treatment by WHO ATC level 1 term, ATC level 3 term and generic drug name, with frequency and percentage of subjects in each dosing arm using each prior medication and each concomitant medication. At each level of subject summarization, a subject is counted once if he/she reported one or more medications at that level. Each summary will be ordered alphabetically by each level of ATC class and by generic drug name within each level of ATC class. Prior and concomitant medications will also be listed separately with these elements as well as the verbatim drug name.

The overall summary and subsets of prior and concomitant medications will be provided for the Safety Set, FAS and PPS.

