Adverse events will be coded to System Organ Class (SOC) and preferred term using MedDRA (version 19.0). The tabular summaries will be provided for AEs, with the number and percentage of subjects reporting each type of event presented by each treatment group and placebo. If a subject reports the same preferred term more than once, it is counted only once within that category. Further, for a given tabulation, the preferred term will only be counted once at its worst severity and strongest relationship to treatment.

Any adverse event which occurs after first administration of the IMPs or pre-existing adverse event which worsens (adverse change in intensity, frequency, or quality) after first administration of the IMPs compared to the complaint present before first intake of the IMPs is considered as a TEAE.

TEAEs will be summarized for each treatment group by SOC and Preferred Term. Additional summaries by time to onset, duration, intensity, relationship to IMP (Related/Not Related), outcome, expectedness, and countermeasures will also be produced. Events reported as "Conditional/Unclassified", "Assessable/Unclassifiable", "Possible", "Probable/Likely", or "Certain" will be included in the Related category. Events reported as "Unlikely Related" or "Not Related" will be included in the Not Related category. Expectedness will be assessed by the sponsor. An unexpected adverse event is one where the nature or intensity is not consistent with the information in the investigator's brochure. Definition of intensity (mild, moderate, or severe) and countermeasures (none, newly started medication, trial discontinuation, or other) is described in the protocol Section 12.3.1.

Subjects with SAEs will be summarized and additionally listed. Special attention will be given to those subjects who discontinue treatment due to an adverse event or who experience a severe adverse event or SAE.

The incidence of all adverse events and TEAEs leading to premature discontinuation from treatment will be presented descriptively.

Selected subset of adverse events

Selected adverse events of interest will be summarized in a separate table:

- Nausea
- Vomit
- Abdominal Pain
- Gastrointestinal Bleeding
- Dizziness
- Hypotension

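### SAP 5.3 sets no upper limit on partly missing stop dates and does not check imputed start dates against a recorded stop

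*SAP*

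**What the plan says.** SAP 5.3 gives these rules for adverse event and medication dates that are needed in a calculation:

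- Stop date, day missing: "For missing stop day only - Day will be imputed as the last day of the month (i.e., 28, 29, 30, or 31".
- Stop date, day and month missing: "Day and month will be imputed as the last day of the year (i.e., 31 December".
- End date wholly missing: "a completely missing end date will be imputed as study completion date".
- Start date wholly missing: "A completely missing start date will be imputed as first dose date of study medication".
- Start date partial, in the same month (or the same year, if the month is also missing) as the reference date, such as first dose or consent: "then the partial date will be imputed to equal the date being used for the calculation".

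No upper bound is stated for a partly missing stop date. No start rule refers to a recorded stop date.

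The results feed three places:

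- SAP 10.1 promises "Additional summaries by time to onset, duration, intensity" and further breakdowns of treatment-emergent events.
- Treatment-emergent status depends on onset relative to first dose (SAP Definitions table and 10.1).
- SAP 7.12 and 10.4 separate prior from concomitant medication by whether the drug was stopped before surgery. Thus "all medications used 14 days prior to enrollment and up to the time of surgery are considered prior medications", and a drug not stopped by then, or newly added later, is concomitant.

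SAP 5.6 allows a blinded review of missing or partial dates if thought necessary. It gives no rule for resolving them.

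**The concern.** Month-end and year-end imputation suits long studies. Here a subject is in the trial for roughly two to three and a half weeks, so the imputed stop will often fall after anyone last saw the subject. The rules also conflict in their logic: less information (no end date at all) gives a bounded date, and more information (a month or a year) gives an unbounded one.

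The start rule has the opposite gap. Adverse events are recorded from consent, up to 10 days before dosing, so an event can begin and end before exposure. If its start is missing, the rule puts the onset on the first-dose date even when the recorded stop shows that the event was already over.

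At stake are the planned duration and time-to-onset summaries and the split between treatment-emergent and pre-treatment events. In Appendix C that split is Tables 14.3.1.2 and 14.3.1.12 on one side and 14.3.1.3 and 14.3.1.11 on the other. The prior and concomitant medication tables (14.1.7 and 14.1.8) are also exposed.

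**Working it through.** **Inputs.** Duration in days is end date − start date + 1 (SAP 5.2). Study day has no Day 0 (SAP 5.2). Enrollment is Day −10 to Day −1 (SAP 3). Scheduled last contact is 13 days after surgery, that is Day 14 (Protocol 11.1.3). The imputation rules are those of SAP 5.3. Calendar dates below are illustrative.

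**1. The plan's own figure.** The SAP expects about 14 to 24 days per subject. Day −10 to Day 14 is 10 + 14 = 24 days inclusive. Day −1 to Day 14 is 14 days elapsed (15 inclusive). The figure is reproduced, and it is the yardstick for a plausible on-trial duration.

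**2. Partly missing stop.** Take first dose and onset on 3 March, so Day 14 is 16 March.

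| Stop date recorded as | Imputed stop | Duration |
|---|---|---|
| wholly missing, study completed on Day 14 | 16 March | 16 − 3 + 1 = 14 days |
| month and year only | 31 March | 31 − 3 + 1 = 29 days |
| year only | 31 December | 304 days (day 365 − day 62 + 1) |

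**3. Dependence on the calendar date.** The rules were applied to every first-dose date in a 365-day year, with onset on Day 1, a true stop on each of Days 1 to 14, and last contact on Day 14.

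- Month-end rule: the stop falls after last contact in about 75% of combinations, by up to 30 days, with durations up to 44 days.
- 31 December rule: about 98% of combinations, by up to 364 days, with a mean duration of 189.5 days and a maximum of 378.

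These shares assume uniformly spread dates and apply only to records with a partial stop date. They are not forecasts for the trial.

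**4. Missing start, recorded stop before dosing.** The start becomes the first-dose date. A stop on Day −k lies k days earlier, so the duration is −k + 1:

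- Day −10: −9 days
- Day −5: −4 days
- Day −1: 0 days

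A partial start behaves the same way. With first dose on 15 March, start recorded as March only and stop recorded as 10 March, the start becomes 15 March when first dose is the reference date, and the duration is 10 − 15 + 1 = −4 days.

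**5. Treatment-emergent status.** The SAP Definitions table counts events from the start of study treatment onward, so an onset imputed to the first-dose date qualifies. SAP 10.1 and Protocol 14.6.1 require occurrence after first administration, which leaves an onset imputed to that date unclear.

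**6. Medication.** Take surgery on 15 January and a drug truly stopped on 10 January, with the stop recorded as January only. The imputed stop is 31 January, after surgery. If status is derived from the imputed date, the drug is concomitant. That can also move the subject between the concomitant-medication subgroups in Tables 14.3.1.22 and 14.3.1.23.

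**7. With the bounds added.** If last actual contact is Day 14, a Day 1 onset lasts at most 14 days and a Day −10 onset at most 24. If no imputed start falls after a recorded stop, the shortest duration is 1 day.

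**The case against.** The strongest reply is that this will hardly ever matter. Start and end date and time are CRF fields for adverse events (Protocol 12.3.1). Missing and inconsistent entries trigger queries that must be resolved before lock (Protocol 13.3). A stop known only by year is remote in so short a trial. Listings show partial dates without imputation, SAP 5.6 permits a blinded review, and Appendix C lists no table of adverse event duration or time to onset. Setting an unknown start to first dose is a usual conservative choice. All of this stands as a limit on size. It does not supply a rule: the review is discretionary, the summaries would use the imputed dates, and the conservative default loses its justification once a recorded stop precedes dosing.

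Four stronger inferences are tempting, and the documents do not support them.

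- **Day 14 is an absolute maximum.** Protocol 12.3.1 follows adverse events to resolution, stability or a clinical judgement that no more evaluation is needed, and Protocol 11.1 allows unscheduled visits. A stop after Day 14 can be genuine.
- **False treatment-emergent events are certain.** They follow from the Definitions table, but SAP 10.1 is ambiguous. That the start rules apply despite an earlier recorded stop is inferred from the absence of an exception; SAP 5.3 does not say so outright.
- **A drug with a known pre-surgery stop and an unknown start drops out of the prior-medication table.** SAP 7.12 and 10.4 classify by the stop relative to surgery, so it remains prior. The imputed dates merely contradict each other.
- **Imputed drug dates distort the prohibited-medication review.** SAP 5.6 describes that review without any mention of imputed dates.

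**Conclusion.** The point holds as a minor defect. Followed as written, SAP 5.3 can produce stop dates beyond last contact, zero or negative durations, and pre-dose events counted as treatment-emergent under one of the SAP's two definitions. It can also turn a prior drug into a concomitant one when only the stop day is missing.

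Each affected record can be badly wrong: 29 or 304 days instead of at most 14 in the worked example. The documents give no frequency of partial dates, and few are expected. The affected outputs are descriptive safety and medication summaries. TOTPAR4 and its four tests do not use these rules.

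The conclusion assumes that the rules are programmed literally, that nobody intervenes under SAP 5.6, and, for medication, that prior or concomitant status is derived from dates and not taken from the site's own entry.

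**What to change.** Add two rules to SAP 5.3:

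1. A partly missing stop date is set to the earlier of the date given by the present rule and the subject's last actual contact, including any adverse event follow-up. The result must not contradict the recorded month or year. For example, a stop recorded as February is not pulled back to a last contact on 28 January.
2. An imputed start date may not be later than a recorded stop date. An adverse event whose recorded stop precedes first dose is not treatment-emergent.

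No separate rule for medications with an unknown start is needed, because the stop date already settles their class. The cost is a short SAP edit and some extra logic and testing in the date macro.
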